10 ANALYSIS POPULATIONS

The main population for non-safety analysis will be the full analysis set (FAS). The Per-Protocol (PP) Population will be used only for the analysis of the primary endpoint to examine the robustness of the primary analysis. As there is not expected to be major differences between the FAS and PP Population for this study the PP Population will only be assessed if there are more than 10 subjects excluded from the PP Population.

Safety data will be analyzed using the Safety Population.

10.1 Full Analysis Set

The FAS consists of all the randomized subjects who had at least one post-randomization product use experience, if randomized to THS 2.2 or CC, and have at least one valid BoExp measurement (THS 2.2, CC, SA arms).

10.2 Per Protocol Population

The PP Population is a subset of FAS and includes all randomized subjects who:

- Have no major protocol deviation to product compliance as defined in **Table 14** if randomized to THS 2.2 or SA.
- Have not been misrandomized.
- Have no other major protocol deviation.*

*Subjects with major protocol deviations that impact the validity of the evaluation of the results (see Section 11“**Protocol Deviations**”) will be excluded in the PP Population.

10.3 Safety Population

The Safety Population consists of all the subjects who had at least one exposure to THS 2.2 (product test at Admission Day). Subjects in the Safety Population will be analyzed according to actual exposure.

11 PROTOCOL DEVIATIONS

Protocol deviations are defined as those deviations from any procedure as defined in the Study Protocol, including but not limited to, as any violation of inclusion/exclusion criteria, mis-randomizations, use of any nicotine or tobacco-containing product other than the assigned product during each of the exposure period, assessments not performed or performed outside the scheduled time windows, or drugs that are known to affect CYP2A6 activity.

Information following site monitoring and other reviews will be documented in the site visit reports, follow-up letters, audit documentation, or other manual review and subsequently recorded in an electronic data capture (EDC) system. Additional protocol deviations may be identified in the data, these will also be recorded in the EDC system.

All deviations will be reviewed to determine their severity/impact when subjects are assigned to analysis populations. Each deviation will be classified as major or minor; all major deviations will be further reviewed to determine whether or not the deviation impacts the evaluability of the results and therefore should result in the subject being excluded from the PP Population.

11.1 Major Protocol Deviations

Subjects with major protocol deviations will be identified (at a population level) to determine whether they will be excluded from any of the analysis populations. This will take place during the pre-analysis data review meeting prior to database lock. The following have been identified as the major protocol deviations.

The categories for the major deviations will include, but are not limited to the deviations presented in Table 14.

Table 14: Definition of Major Protocol Deviations

Category	Description
Mis-randomization	Being administered the wrong product according to the randomization schedule. Use of any nicotine or tobacco-containing product other than the assigned product.
Product compliance Violation	Exhaled CO breath test >10 ppm for subjects from the SA arm after Day 2
Duration of 24 hour collection	Violation of inclusion/exclusion criteria. Start and end times not within the 30 min window.

Among the above criteria, violations of inclusion criteria 5 to 7, or of the exclusion criteria 1, 3 to 16, and 18 will be assessed for their impact on the PP Population and evaluated during the pre-analysis data review meeting (Section 6.3.1 “Methods of Assigning Subjects to Product Arms”).

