- CC Arm: 40 subjects, *ad libitum* use of their preferred CC brand.
- SA Arm: 40 subjects who will abstain from smoking.

Subjects will be informed of their randomized study arm by the study site collaborator on Day 1 prior to 06:30 AM.

- Exposure period (from Day 1, 06:30 AM until Day 5, 11:00 PM):

The exposure period will consist of 5 days of *ad libitum* use of the assigned product between 06:30 AM and 11:00 PM in THS 2.2 and CC arms. Use of any tobacco/nicotine containing product other than the assigned product will not be allowed and may, at the discretion of the Investigator, result in the subject withdrawal from the study.

Subjects in the SA arm will be asked to abstain from smoking any nicotine/tobacco containing product and will not be provided with medication to support SA.

The end of the 24-h urine collection period for Day 5 will end in the morning on Day 6 prior to Discharge.

- Day of Discharge (Day 6) (from Day 5, 11:01 PM to time of Discharge):

Procedures of Discharge, including but not limited to laboratory parameters, will be conducted to discharge the subject from the clinic after 9 days in a confined setting. Use of CC will be allowed on Day 6, but only after spirometry has been performed.

- Safety follow-up period (from the time of Discharge on Day 6 to Day 13):

After time of Discharge, subject will enter a 7-day safety follow-up during which there will be recording of spontaneously reported new AEs/SAEs and the active follow-up of ongoing AEs/SAEs by the study site. In general, all AEs will be followed until resolved, stabilized (i.e., no worsening of the event), or a plausible explanation for the event has

been found. The end of the study is defined as the time of Discharge on Day 6 plus 7-day follow-up period.

During the study, any subjects who want to quit smoking will be encouraged to do so, and will be referred to medical services and will be withdrawn from the study. This is applicable for all subjects during screening to the baseline period and for subjects allocated to THS 2.2 or CC arms during the exposure period.

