6.2.3.3 Smoking Abstinence Arm

Subjects randomized to the SA study arm will be instructed to abstain from smoking from Day 1, 06:30 AM onwards until Day 5, 11:00 PM. They will not be provided with medication supportive for smoking abstinence.

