7.5.1 Biomarker of Exposure

7.5.1.1 Exhaled CO and Carboxyhemoglobin

Carboxyhemoglobin measured in blood and exhaled CO will be investigated as a measure of CO in all three study arms. The CO breath test should be conducted in timely conjunction with the blood sampling for COHb, where applicable. In the SA arm, the CO breath test will serve as a verification of compliance (Section 6.5.4).

CO Breath Test

Carbon monoxide in exhaled breath will be measured using the Smokerlyzer[®] such as Micro 4 Smokerlyzer[®] device or similar.

On Days -1 to Day 5, the CO breath test will be conducted four times per day. The first test should be conducted within 15 minutes prior to the first product use. The other three tests should be conducted as described in section 9.

Confidentiality statement: Data and information contained in this document are considered to constitute trade secrets and confidential commercial information, and the legal protections provided to such trade secrets and confidential information are hereby claimed under the provisions of applicable law. No part of this document may be publicly disclosed without the written consent of Philip Morris Products S.A.

For subjects in the SA arm, the first CO breath test will be done between 08:00 AM-09:30 AM. The other three tests should be conducted as described in section 9.

On Day -2, Day 6, the CO breath tests will be conducted once irrespective of time of product use.

Carboxyhemoglobin

Assessment for COHb measurement will be performed at the local laboratory. Carboxyhemoglobin in blood will be assessed on a daily basis, starting from Day -1 until Day 5.

On Day -1 to Day 4: one blood sample will be collected between 08:00 PM-09:30 PM.

On Day 5: one blood sample will be collected within 15 minutes prior to the first product use. The three other blood samples will be collected as described in section 9.

For subjects in the SA arm, the first COHb will be done between 08:00 AM-09:30 AM. The three other blood samples will be collected as described in section 9.

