6.1.1 Timing of Confinement Period

The 9 day confinement period consists of:

- The Admission Day (Day -2).
- The run-in period, from Admission on Day -2 until 06:29 AM of Day -1.
- The baseline period, from Day -1, 06:30 AM until Day 1, 06:29 AM.
- The exposure period, from Day 1, 06:30 AM until Day 5, 11:00 PM.
- The day of Discharge, Day 6, from Day 5 (11:01 PM) to time of Discharge on Day 6.

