**Table 16: Assessment Windows**

Assessment	Nominal Time point(s)	Window
CO breath test	Day -2 and Day 6 Morning (Days -1 to 5)	Irrespective of product use To be done within 15 minutes prior to product use (for THS 2.2 and CC arms) or between 08:00 AM and 09:30 AM (SA arm)
	Day -1 to Day 5	Between 12:00 PM and 01:30 PM, 04:00 PM and 05:30 PM, and 08:00 PM and 09:30 PM
Assessment of Cough	Day 0 to 6	To be done prior to smoking/product use but not later than 10:00 AM.
MNWS Questionnaire	Day 0 to 6	To be done prior to product use but not later than 10:00 AM
QSU-brief questionnaire	Day -1 to 5	08:00 PM to 11:00 PM
MCEQ questionnaire	Day -1 to 5	08:00 PM to 11:00 PM
Nicotine and cotinine in plasma	Day 0 to Day 4 (all study arms) between 08:00 PM and 09:30 PM	
	Day 5 (THS 2.2 and CC arms) within 15 minutes before first product use (T_0): then additional blood samples at 2 hour intervals from T_0 until 11:00 PM.	Each sample has a 5 minute time window
	Day 6 (THS 2.2 and CC arms): 20 and 24 h after T_0 of Day 5 Day 5 and Day 6 (SA arm): On Day 5, between 08:00 PM and 09:30 PM. On Day 6, between 08:00 AM and 9:30 AM.	5 minute time window
COHb blood Sampling	Days -1 to 4 Morning sample on Day 5	8:00 PM to 09:30 PM Within 15 minutes prior to product use (for THS 2.2 and CC arms) or between 08:00 AM and 09:30 AM (SA arm)
	Day 5 other samples	Between 12:00 PM and 01:30 PM, 04:00 PM and 05:30 PM, and 08:00 PM and 09:30 PM

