12.4 Measurements of Product Compliance

During the confinement period, compliance to product/regimen allocation (exclusive use of THS 2.2 and CC in THS 2.2 and CC arms, respectively, and full abstinence from smoking in the SA arm) will be ensured by strict distribution of each THS Tobacco Stick/CC when requested by the subject.

In addition, levels of CO in exhaled breath will be measured in the SA arm to ensure that the subjects have not smoked any cigarettes. This will serve as a compliance tool during the confinement period. These data (continuous and categorical) will be summarized and listed by actual exposure.

The data will be presented in the below outputs, the TFL number refers to the TFL number in the accompanying TFL shell document:

TFL number	Title
TABLES	
15.2.5.1	Summary of Compliance as Measured by Exhaled CO (ppm) in the SA Arm- Safety Population
LISTINGS	
15.3.3.2	Listing of Secondary Biomarkers and Sampling/Collection Times

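### Two major-deviation rules in SAP Table 14 (breath CO in the SA arm, timing of 24-hour urine) conflict with the schedule, so subjects can be misclassified as major deviators and per-protocol membership misassigned, subject to the pre-lock review

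*SAP*

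**What the plan says.** **Breath CO.** SAP 11.1, Table 14, lists "Exhaled CO breath test >10 ppm for subjects from the SA arm after Day 2" as a major deviation in product compliance. Protocol 7.5.1.1 schedules a test on the day of discharge: "On Day -2, Day 6, the CO breath tests will be conducted once irrespective of time of product use". SAP Table 16 gives the same test the window "Irrespective of product use". SA subjects are told to "abstain from smoking from Day 1, 06:30 AM onwards until Day 5, 11:00 PM" (Protocol 6.2.3.3). Protocol 4.1 adds: "Use of CC will be allowed on Day 6, but only after spirometry has been performed". Protocol 6.6.1 likewise bans smoking from 11:00 PM on Day 5 only until that spirometry.

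**Urine.** Table 14 makes a 24-hour collection a major deviation for "Start and end times not within the 30 min window". SAP Table 16 and the daily schedules in Protocol 9.2 give ±20 minutes for the start and the end.

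**Use of the rules.** The first PP criterion in SAP 10.2 removes THS 2.2 and SA subjects who have a product-compliance deviation as listed in Table 14. For other major deviations, a footnote limits exclusion to those that affect validity. SAP 11 has all major deviations reviewed before lock. SAP 10 assesses the PP population only if more than 10 subjects are excluded from it.

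**The concern.** A deviation rule should flag departures from what the protocol requires. The CO rule has a start and no end, so it reaches a reading that permitted smoking can raise. The 10 ppm cut-off separates cigarette use from no use (SAP 6.3.3), so it says nothing about compliance once cigarettes are allowed. An SA subject who abstained fully through Day 5 could be listed as a major deviator, and could count towards the trigger for the PP analysis.

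The urine rule refers to a window that is not in the documents. The text does not say whether 30 minutes means ±30, a total width of 30, or a tolerance on duration. Whether the rule is looser or stricter than the schedule therefore cannot be told.

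At stake are the deviation tables, the SA compliance summary (Table 15.2.5.1), PP membership and the PP trigger.

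**Working it through.** The plan gives no figure for this point, so the check compares the texts and adds some arithmetic.

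**1. Does the CO rule reach Day 6?**
- Rule: after Day 2, no last day (SAP Table 14).
- Scope of the tool: "This will serve as a compliance tool during the confinement period" (SAP 12.4). SAP 6.1.1 counts Day 6 in confinement: "The day of Discharge, Day 6, from Day 5 (11:01 PM) to time of Discharge on Day 6".
- Order on Day 6 (Protocol Table 15): CYP2A6 sampling, cough, MNWS and spirometry are marked as before smoking. The CO test is marked only as before discharge.
- So the literal rule covers a test that can come after permitted smoking.

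**2. What does closing the rule cost?** CO is tested four times a day up to Day 5 and once on Day 6. Taking the rule to begin on Day 3, Days 3 to 5 give 3 × 4 = 12 readings. Ending it at Day 5, 11:00 PM drops 1 reading per SA subject.

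**3. Trigger.** More than 10 means at least 11. 11/40 = 27.5% of the SA arm; 11/160 = 6.9% of all randomized subjects. This is the size needed for Day 6 flags alone to start the PP analysis, not a forecast.

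**4. Effect on THS 2.2 versus CC in the PP set.** SA subjects enter only through the common covariates and the residual variance (SAP 12.6 keeps all arms in the models). Inputs for COHb from SAP Table 11: mean ratio 0.40, CV 0.32, 80 versus 40 subjects, one-sided 2.5%, 50% margin.
- Log-scale SD = √ln(1 + 0.32²) = 0.312
- Distance to the margin = ln(0.50/0.40) = 0.223
- SE = 0.312 × √(1/80 + 1/40) = 0.0605

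As a check on the method, the four Table 11 biomarkers taken as independent give joint power 0.955 (noncentral t, 118 df), against 96% in SAP Table 13. For COHb alone:

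| SA subjects in model | Residual df | Power |
|---|---|---|
| 40 | 160 − 6 = 154 | 0.9561 |
| 29 | 149 − 6 = 143 | 0.9560 |
| 0 | 120 − 5 = 115 | 0.9554 |

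**5. Urine windows.** Nominal duration is 06:30 AM to 06:29 AM, 23 h 59 min = 1,439 min. With a tolerance of w minutes at each end, duration runs from 1,439 − 2w to 1,439 + 2w.

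| Reading | w | Duration (min) | Deviation |
|---|---|---|---|
| Schedule, ±20 | 20 | 1,399 to 1,479 | 40/1,439 = 2.8% |
| 30 as ±30 | 30 | 1,379 to 1,499 | 60/1,439 = 4.2% |
| 30 as total width | 15 | 1,409 to 1,469 | 30/1,439 = 2.1% |

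Read as ±30, times more than 20 and up to 30 minutes off breach the schedule but are not major. Read as a total width, times more than 15 and up to 20 minutes off meet the schedule but are major, although Protocol 9 says measurements within the window are not deviations. A further 10 minutes at one end is 10/1,439 = 0.7% of the collection. The three urinary primary endpoints are ratios to creatinine from the same collection (SAP 7.1.1), so they should move little.

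**The case against.** The strongest reply is that Table 14 does not act alone. SAP 11 ties product-use deviations to the exposure period, which ends on Day 5 at 11:00 PM, and has all major deviations reviewed before lock. Reviewers therefore have grounds to set a Day 6 reading aside. This stands, and it rules out a conclusion that a reader might draw, that PP membership must come out wrong. It does not cure the rule. The first PP criterion takes product-compliance deviations straight from Table 14, and the validity footnote is attached only to other major deviations. The sponsor also receives blinded data for the pre-analysis review (SAP 6.3.2), so a rule specific to one arm should be right as written. The only change listed for SAP version 2.0 concerns which early days this same rule covers; the late end stayed open.

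On urine, ±20 minutes as the schedule and a wider limit for major deviations is a coherent two-tier design. That is possible, but nothing states it. Nor does the missing urine row in SAP Table 15 leave a late collection unclassified, as a reader might infer: the lists are not exhaustive, and SAP 11 has every deviation classed as major or minor. It is also tempting to say that the window decides which collections are valid for three primary biomarkers. The PP rules exclude subjects, not collections, and for urine timing only after a judgement on validity.

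On consequences, the planned PP tables (15.2.4.1 to 15.2.4.4) all compare with CC, and the comparison of primary biomarkers with SA uses the full analysis set. A false trigger would add one robustness analysis, which SAP 12.6.2.1 describes without any condition. All of this stands and limits the point.

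**Conclusion.** Both mismatches are in the text. Subjects can be misclassified as major deviators and PP membership can be misassigned; whether this happens depends on the pre-lock review. The effect is confined to deviation and compliance reporting, PP membership and the more-than-10 trigger. The primary analysis on the full analysis set is untouched. The effect on the PP contrast of THS 2.2 with CC is negligible: under the COHb planning inputs, power stays between 0.955 and 0.956 even with every SA subject removed.

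The number of subjects affected cannot be estimated. A reader might take the 40 SA subjects as the size of the problem, but that is only the size of the arm. The documents do not say how many would smoke between spirometry and the Day 6 test, or whether doing so would take CO above 10 ppm. Table 15.2.5.1 is affected only if the Day 6 reading goes into it, which the SAP text does not settle. The direction of any urine misclassification depends on what 30 minutes was meant to be.

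**What to change.** 1. In SAP Table 14, limit the CO criterion to SA-arm tests after Day 2 up to the end of required abstinence at 11:00 PM on Day 5. Do not use the Day 6 reading as a compliance measure in Table 15.2.5.1; it can still be listed.
2. Reconcile the urine rule with the schedule. Either use the ±20-minute window of Table 16, or state two tiers: beyond ±20 and up to ±30 minutes is minor, with a row added to SAP Table 15, and beyond ±30 minutes is major.

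The cost is a few phrases in the SAP before database lock, with no change to data collection. The CO change gives up one reading per SA subject. If 30 minutes was meant as ±30, the single ±20-minute rule would class more collections as major deviations; the two-tier wording avoids that. If lock has passed, the readings applied should be reported in the clinical study report, as SAP 3 provides for changes to the analyses.

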11.2 Minor Protocol Deviations

The categories for the minor deviations will include, but are not limited to the deviations presented in Table 15.

Table 15: Definition of Minor Protocol Deviation Categories

Category	Description
Concomitant medication	Use of drugs which are known to affect CYP2A6 or CYP1A2 activity.
Time deviation (Questionnaires)	Assessments not taken at the correct time or within the allowed time window (see Table 16)
Time deviation (Blood draws)	Assessments not taken at the correct time or within the allowed time window (see Table 16)
Time deviation (CYP1A2 activity)	Assessments not taken at the correct time or within the allowed time window (see Table 16)
Time deviation (CYP2A6 activity)	Assessments not taken at the correct time or within the allowed time window (see Table 16)
Time deviation (Assessment of cough)	Assessments not taken at the correct time or within the allowed time window (see Table 16)
Time deviation (CO breath test)	Assessments not taken at the correct time or within the allowed time window (see Table 16)
Time deviation (HST Recording)	Assessments not taken at the correct time or within the allowed time window (see Table 16)
Time missing	Assessment date or time is missing
Assessment missing	Assessment is missing
Visit missing	Scheduled visit not done

11.3 Assessment Windows

Smoking of the randomized products should take place within the 06:30 AM and 11:00 PM window.

The assessment windows are shown in Table 16.

Table 16: Assessment Windows

Assessment	Nominal Time point(s)	Window
24 h urine sample	Start (All days)	06:30 AM \pm 20 min
	End on the following day (All days)	06:29 AM \pm 20 min
CYP1A2 activity in plasma	Start (Days 0 and 5)	6 hours after intake of caffeine tablet \pm 15 min
CYP2A6 activity	Day 0 and Day 6	Prior to smoking / product use

**Table 16: Assessment Windows**

Assessment	Nominal Time point(s)	Window
CO breath test	Day -2 and Day 6 Morning (Days -1 to 5)	Irrespective of product use To be done within 15 minutes prior to product use (for THS 2.2 and CC arms) or between 08:00 AM and 09:30 AM (SA arm)
	Day -1 to Day 5	Between 12:00 PM and 01:30 PM, 04:00 PM and 05:30 PM, and 08:00 PM and 09:30 PM
Assessment of Cough	Day 0 to 6	To be done prior to smoking/product use but not later than 10:00 AM.
MNWS Questionnaire	Day 0 to 6	To be done prior to product use but not later than 10:00 AM
QSU-brief questionnaire	Day -1 to 5	08:00 PM to 11:00 PM
MCEQ questionnaire	Day -1 to 5	08:00 PM to 11:00 PM
Nicotine and cotinine in plasma	Day 0 to Day 4 (all study arms) between 08:00 PM and 09:30 PM	
	Day 5 (THS 2.2 and CC arms) within 15 minutes before first product use (T_0): then additional blood samples at 2 hour intervals from T_0 until 11:00 PM.	Each sample has a 5 minute time window
	Day 6 (THS 2.2 and CC arms): 20 and 24 h after T_0 of Day 5 Day 5 and Day 6 (SA arm): On Day 5, between 08:00 PM and 09:30 PM. On Day 6, between 08:00 AM and 9:30 AM.	5 minute time window
COHb blood Sampling	Days -1 to 4 Morning sample on Day 5	8:00 PM to 09:30 PM Within 15 minutes prior to product use (for THS 2.2 and CC arms) or between 08:00 AM and 09:30 AM (SA arm)
	Day 5 other samples	Between 12:00 PM and 01:30 PM, 04:00 PM and 05:30 PM, and 08:00 PM and 09:30 PM

**Table 16: Assessment Windows**

Assessment	Nominal Time point(s)	Window
HST Questionnaire	Day 0	08:00 PM-09:30 PM
	Day 4 for all subjects in the THS 2.2 and CC arms smoking compatible CC	08:00 PM-08:30 PM
HST Recording	Day 0	06:30 AM-09:30 PM
	Day 1 and Day 4 for all subjects in the THS 2.2 and CC arms smoking compatible CC	06:30 AM-09:30 PM

12 PLANNED STATISTICAL METHODS

12.1 General Considerations

Data analysis will be performed using SAS[®] Version 9.2 or higher.

Data listings will be provided for all data collected as required by this protocol, ordered by actual exposure and subject and time point (if applicable), unless otherwise stated. Summary statistics and statistical analysis will only be presented for data where detailed in this SAP. All unscheduled assessments will be included in the listings.

Safety data will be summarized for the Safety Population, biomarker data will be summarized and analyzed for the FAS unless otherwise stated.

